#### **5.1.5 Intra-Patient Dose Adjustment**

Patients may be permitted an intra-patient dose-escalation of AC176 to a higher dose level that has been cleared and deemed safe by the SRC if they have completed at least 2 cycles at their assigned dose level and continued on study with no  $\geq$  Grade 2 treatment-related AEs. The highest dose the patient can be escalated to is the highest dose level that has been cleared for DLT and is considered to be safe for this patient by the Investigator. The Investigator must consult with the Medical Monitor to confirm that the patient has been tolerating their AC176 dose. The patient data will continue to be collected for evaluation of safety and clinical activity, and all assessments will continue according to the Schedule of Assessments (see applicable SOA Table 2 or Appendix H).

*CONFIDENTIAL*

Study Drug: AC176

Sponsor/Development Innovations Study Number: AC176-001/GU 207

Final Protocol: 10 July 2023 Version 4.0

### **5.1.6 Safety Review Committee**

After each dose level during the dose-escalation, an SRC will evaluate the safety, tolerability, and available PK data for AC176 to decide the next dose. The SRC has discretion to consider the MTD or other doses as the RP2D. However, the RP2D will be no greater than the MTD.

The SRC will consist of:

- Coordinating Investigator, who will chair the committee, or delegate
- Principal Investigator or delegate from the Investigational sites
- Medical Monitor(s) for the study or delegate(s).

In addition, the Sponsor Safety Physician or delegates(s) may be invited. The Study Pharmacologist, Study Statistician, Patient Safety Scientist, Project Manager and other experts may also be invited as appropriate.

Further internal or external experts may be consulted by the SRC as necessary. The Sponsor Safety Physician (if applicable), Medical Monitors, or delegates should always be present at the SRC if there are safety issues for discussion. The SRC will be consulted throughout the study on issues related to study safety.

### **5.1.7 Expansion Cohorts (Part B)**

The recommended dose for the Expansion Cohorts will be determined in the Part A Dose-Escalation part of the study. The opening of the Expansion Cohorts will be determined by the Sponsor after review of the emerging safety and tolerability data from the dose-escalation phase. Two cohorts may be explored in Part B and will involve approximately 30 patients each with AR point mutations and 30 patients without AR point mutations. The Sponsor and SRC will determine the dose, schedule (e.g., BID dosing, intermittent scheduled dosing days, change in number of days in a cycle) and cohort open time for the expansion phase.

## **5.2 Treatment Duration**

The **start of the study** is defined as the date when the first patient in the whole study signs informed consent.

The **end of the study** is defined as the date of the last visit (including all follow-up visits) of the last patient in the whole study.

Patients will be evaluated for toxicity at the start of each cycle. Restaging will occur with CT/MRI or bone imaging as defined in the applicable SOA (see [Table 2](#) or [Appendix H](#)). Patients will continue on treatment until disease progression as defined in [Appendix B](#) and [Appendix C](#) or intolerance of side effects.

## **5.3 Concomitant Medications**

Patients will be asked about prior medications during screening and instructed not to take any additional medications during the course of the study without prior consultation with the study team. At each visit, the patient will be asked about any new medications he or she is taking or has taken after the start of study drug treatment. The patients will be asked to take AC176 in the morning immediately after a meal, and other concomitant medications in the evening; or at least 4 hours apart from taking AC176, if possible.

*CONFIDENTIAL*

Study Drug: AC176

Sponsor/Development Innovations Study Number: AC176-001/GU 207

Final Protocol: 10 July 2023 Version 4.0

### **5.3.1 Permitted Concomitant Medications**

Supportive care per institutional standard, such as anti-emetics, is allowed during the study.

Medications may be administered for maintenance of existing conditions prior to study enrollment or for a new condition that develops while on study, including but not limited to the following:

- Bisphosphonate use, as recommended according to practice guidelines
- Receptor activator of nuclear factor kappa-B ligand (RANKL) inhibitor use, as recommended according to practice guidelines
- Growth factors or transfusions are allowed as clinically indicated, except the 2 weeks prior to the first dose of study treatment and during the Cycle 1 DLT evaluation period.
- Patients receiving coumarin-derivatives are permitted on study but will be monitored carefully. Should a thrombotic event occur while the patient is receiving treatment, the patient may continue, but low-molecular-weight heparin (LMWH) will be the preferred treatment.

Supportive care and other medications considered necessary for the patient's safety and well-being may be given at the discretion of the Investigator, with the exception of those listed in Section [5.3.2](#).

### **5.3.2 Prohibited Concomitant Medications**

The following treatments are prohibited while on this study:

- No other investigational therapy should be given to patients. No anticancer agents other than the study treatments should be given to patients. If such agents are required for a patient, then the patient must first be withdrawn from the study.
- No routine prophylactic antiemetics or pre-medications will be given. However, these medications may be administered for symptoms when they occur and may be given prophylactically afterward.

## **6. DOSE MODIFICATIONS**

If toxicity occurs, it will be graded using the NCI [CTCAE Version 5.0](#), and appropriate supportive care treatment will be administered to decrease the signs and symptoms thereof. Dose adjustments will be based on the organ system exhibiting the greatest degree of toxicity. Patients who experience a DLT during Cycle 1 can continue on the study at the next lower dose if the toxicity resolves to Grade 1 or baseline.

A dose may be delayed for a patient for up to 2 weeks because of AEs. Continuing treatment after a delay of more than 2 weeks may be allowed if the treating physician and the Medical Monitor agree that continuing treatment is in the best interest of the patient.

Patients whose treatment is delayed will resume treatment when toxicity has improved to  $\leq$  Grade 1 or baseline.

If toxicities occur that are  $\leq$  Grade 2, they should be managed symptomatically, if possible, and the patient should continue treatment without a dose reduction. If toxicities occur that are  $\geq$  Grade 3 refer to [Table 5](#) and [Table 6](#) for dose modification guidelines.

*CONFIDENTIAL*

Study Drug: AC176

Sponsor/Development Innovations Study Number: AC176-001/GU 207

Final Protocol: 10 July 2023 Version 4.0

A maximum of 2 dose reductions are allowed in this study. However, dose reductions below the 30-mg starting dose will not be allowed. If more than 2 dose reductions of AC176 are necessary for a patient, the patient will be discontinued from study treatment, unless the treating physician and the Medical Monitor agree that continued treatment at lower doses is in the best interest of the patient.

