### 5.1.3 Dose-Limiting Toxicity

Toxicity will be assessed using NCI CTCAE Version 5.0 unless otherwise specified.

A toxicity will be considered dose-limiting if it occurs during the first cycle of treatment with AC176 during the dose-escalation phase (excluding Backfill cohort patients). Dose-limiting toxicities (DLTs) will not include any toxicity related to underlying disease (including disease progression), intercurrent illness, concomitant medications, or extraneous causes. DLTs will be defined as follows:

- Any Grade 5 toxicity
- **Hematologic:**
  - Grade 4 neutrophil count decrease for >7 days; or febrile with neutrophil count decrease (ANC <1000/mm^3 with a single temperature of >38.3°C [101°F] or a sustained temperature of ≥ 38°C [100.4°F] for more than 1 hour)
  - Grade 4 platelet count decrease; or Grade 3 platelet count decrease associated with clinically significant bleeding, including any bleeding that warrants a platelet transfusion, related to drug
  - Grade 4 anemia related to drug (life-threatening consequences requiring urgent interventions)
- **Non-Hematologic:**
  - Grade 3 or 4 non-hematologic toxicity, with the **exception of**:
    - Alopecia;
    - Grade 3 nausea, vomiting, or diarrhea if well-controlled by supportive care within 72 hours;
    - Grade 3 skin rash that improves in ≤7 days, with or without supportive care;
    - Grade 3 fatigue that improves in ≤7 days, with or without supportive care;
    - Grade 3 endocrinopathies that only require treatment with hormone replacement therapy;

*CONFIDENTIAL*

Study Drug: AC176

Sponsor/Development Innovations Study Number: AC176-001/GU 207

Final Protocol: 10 July 2023 Version 4.0

- Grade 3 non-hematologic laboratory abnormalities, other than liver function tests, will not be considered a DLT unless they are associated with clinical manifestations which lead to medical intervention and/or hospitalization.
- Potential drug-induced liver injury consistent with Hy's Law (Appendix F), defined as AST and/or ALT  $>3 \times$  ULN with concurrent total bilirubin  $>2 \times$  ULN without findings of cholestasis (alkaline phosphatase [ALP]  $>2 \times$  ULN)
- Grade 3 or higher electrolyte abnormality that lasts  $>72$  hours, unless the patient has clinical symptoms, in which case all Grade 3 or higher electrolyte abnormalities regardless of duration should count as a DLT

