**Table 5 Dose Modifications Due to Hematologic Toxicities**

Event	AC176 Dose a
Neutrophil Count Decrease (ANC)	
ANC $<0.5 \times 10^9/L$ (Grade 4)	Hold dose until recovery to $\leq$ Grade 2 (ANC $\geq 1.0 \times 10^9/L$ ) b , 
 
• If resolved in <math>\leq 7</math> days, then resume without a dose reduction.
 
• If resolved in <math>>7</math> days but <math><2</math> weeks, then resume dose at one lower dose level.
 

Recurrence of ANC $<0.5 \times 10^9/L$ (Grade 4)	Hold dose until recovery to $\leq$ Grade 2 (ANC $\geq 1.0 \times 10^9/L$ ), then resume at 1 lower dose level b .
Platelet Count Decrease	
Platelets $<50 \times 10^9/L$ (Grade 3)	Hold dose until improvement to platelets $\geq 75 \times 10^9/L$ b 
 
• If resolved in <math>\leq 7</math> days, then resume without a dose reduction.
 
• If resolved in <math>>7</math> days but <math><2</math> weeks, then resume dose at 1 lower dose level.
 

Other severe and non-life-threatening toxicities (<math>\geq</math>Grade 3)	Hold or maintain dose at the treating physician's discretion.  Monitor at least weekly and manage accordingly.

a Any patients who require a treatment delay of more than 2 weeks due to treatment-related toxicity will be discontinued from study treatment unless the treating physician and the Medical Monitor agree that continued treatment at lower doses is in the best interest of the patient.

b Hold AC176 treatment; perform at least weekly complete blood count (CBC) with differentials until toxicity resolves (ANC recovery  $\geq 1.0 \times 10^9/L$  and platelets  $\geq 75 \times 10^9/L$ ).

Re-treatment criteria = ANC recovery  $\geq 1.0 \times 10^9/L$  and platelets  $\geq 75 \times 10^9/L$ .

CONFIDENTIAL

Study Drug: AC176

Sponsor/Development Innovations Study Number: AC176-001/GU 207

Final Protocol: 10 July 2023 Version 4.0

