**Table 6 Dose Modifications due to Grade 3 or 4 Non-Hematologic Toxicities**

Toxicity Grade	AC176 Dose a
Grade 3 (except nausea, vomiting, alopecia, diarrhea, rash, and fatigue)	Hold a until recovery to $\leq$ Grade 1 or baseline
Toxicity resolves in $\leq$ 7 days	Resume at original dose.
Toxicity resolves $>$ 7 day and $<$ 2 weeks	Reduce by 1 dose level.
Toxicity does not resolve to $\leq$ Grade 1 or baseline within 2 weeks	Discontinue treatment. If in the patient's best interest, dose may be resumed at a lower dose only after discussion and agreement with Medical Monitor.
Recurrence of the above same toxicity	Hold a until recovery to $\leq$ Grade 1 or baseline
Toxicity resolves $\leq$ 7 days	Resume at original dose or reduce by 1 dose level at the Investigator's discretion b
Toxicity resolves $>$ 7 days	Discontinue treatment. If in the patient's best interest, dose may be resumed at 1 reduced dose level only after discussion and agreement with Medical Monitor
Grade 4 (except asymptomatic electrolyte abnormalities that respond to treatment and resolve to $\leq$ Grade 2 within 72 hours, nausea, vomiting, alopecia, diarrhea, rash, and fatigue)	Discontinue treatment.
Grade 4 asymptomatic electrolyte abnormalities that respond to treatment and resolve to $\leq$ Grade 2 within 72 hours	Hold a Once resolved as mentioned, treatment may continue at 1 reduced dose level at the Investigator's discretion and upon discussion with Medical Monitor
Grade 3 or 4 nausea, vomiting diarrhea, rash, or fatigue	Hold and institute maximum supportive treatment until recovery to $\leq$ Grade 1, baseline or tolerable Grade 2
Toxicity resolves $\leq$ 7 days	Resume at original dose.
Toxicity resolves $>$ 7 day and $<$ 2 weeks	Reduce by one dose level b

Toxicity Grade	AC176 Dose a
Toxicity does not resolve to $\leq$ Grade 1 or baseline, or tolerable Grade 2 by 2 weeks	Discontinue treatment. If in the patient's best interest, dose may be resumed at a lower dose only after discussion and agreement with Medical Monitor
Recurrence of the above same toxicity	Hold and institute maximum supportive treatment until recovery to $\leq$ Grade 1, baseline or tolerable Grade 2
Toxicity resolves $\leq$ 7 days	Resume at original dose or reduce by one dose level at the Investigator's discretion b

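### Section 6 and Tables 5 and 6 conflict, with no stated precedence, on the dose after some Cycle 1 DLTs and on the recovery grade needed to restart

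*Protocol*

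**What the plan says.** Section 6 of the protocol gives a rule specific to DLTs: "Patients who experience a DLT during Cycle 1 can continue on the study at the next lower dose", provided the toxicity has come back to Grade 1 or baseline. It also gives a general rule for any delay: "Patients whose treatment is delayed will resume treatment when toxicity has improved to" Grade 1 or less, or baseline. It then refers toxicities of Grade 3 or higher to Tables 5 and 6, and adds that "dose reductions below the 30-mg starting dose will not be allowed".

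Table 5 (hematologic) has a row for neutrophils below 0.5 × 10⁹/L, labelled Grade 4, and a row for platelets below 50 × 10⁹/L, labelled Grade 3. In both, if recovery takes 7 days or less, "then resume without a dose reduction". The recovery threshold for neutrophils is Grade 2 or better (at least 1.0 × 10⁹/L).

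Table 6 (non-hematologic) has three rows that matter here:
- A first Grade 3 event resolved in 7 days or less: "Resume at original dose".
- A Grade 4 event outside the listed exceptions: treatment is discontinued.
- Nausea, vomiting, diarrhea, rash or fatigue of Grade 3 or 4: the hold ends at Grade 1, "baseline or tolerable Grade 2".

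Footnote a, attached to the dose column of Table 6, requires Grade 1 or baseline.

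Section 5.1.3 makes a Cycle 1 "Grade 3 or 4 non-hematologic toxicity" a DLT, with listed exceptions. Its hematologic DLTs include Grade 4 platelets, Grade 3 platelets with clinically significant bleeding, Grade 4 neutrophils for more than 7 days, and fever with a low neutrophil count.

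**The concern.** Many of the events that Section 5.1.3 counts as DLTs are also events that Tables 5 and 6 cover, and the two sets of instructions do not always agree. Section 6 neither exempts Cycle 1 DLTs from the tables nor says that the tables override its own sentence. Two sites could both follow the protocol and treat the same event differently: one re-exposes the patient at the dose that produced the DLT, the other reduces; or one continues at a lower dose and the other stops.

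The restart conflict reaches further. It applies in every cycle and to every cohort, including Backfill patients, whose toxicity Section 5.1.2 manages under Section 6.

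The data are affected too. Section 10.5.3 has the Safety Review Committee take dose interruptions and reductions into account, and Section 10.4.3 summarizes AEs leading to hold, reduction or discontinuation by dose level. Both would partly reflect which passage a site happened to follow.

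**Working it through.** No arithmetic underlies the main point. The check matches each DLT type in Section 5.1.3 to the action in Section 6 and in the relevant table.

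**Action after a Cycle 1 DLT**

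| Cycle 1 DLT | Section 6 | Table | Agree? |
|---|---|---|---|
| Grade 3 non-hematologic, resolved in ≤7 days | Next lower dose | Table 6: original dose | No |
| Grade 3 non-hematologic, resolved in >7 days and <2 weeks | Next lower dose | Table 6: one level lower | Yes |
| Grade 4 non-hematologic, outside Table 6's exceptions | May continue at next lower dose | Table 6: discontinue | No |
| Grade 4 nausea, vomiting, diarrhea or fatigue, resolved in ≤7 days | Next lower dose | Table 6: original dose | No |
| Grade 3 platelets with significant bleeding, recovered in ≤7 days | Next lower dose | Table 5: no reduction | No |
| Grade 4 platelets, recovered in ≤7 days | Next lower dose | Table 5: unclear | Unclear |
| Fever with neutrophils below 0.5 × 10⁹/L, recovered in ≤7 days | Next lower dose | Table 5: no reduction | No |
| Grade 4 neutrophils, >7 days and <2 weeks | Next lower dose | Table 5: one level lower | Yes |

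The Grade 4 platelet row is unclear because the threshold of below 50 has no lower bound, while the label says Grade 3. If the row covers Grade 4, it gives no reduction. If it does not, the only other candidate is the last row of Table 5, which leaves hold or maintain to the physician.

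A DLT at 30 mg has no next lower dose, because reductions below 30 mg are barred. The Section 6 sentence cannot be followed there.

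**Recovery needed to restart, any cycle**

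| Source | Criterion |
|---|---|
| Section 6, after any delay | ≤ Grade 1 or baseline |
| Table 6 footnote a | ≤ Grade 1 or baseline |
| Table 5, neutrophils | ≤ Grade 2 |
| Table 6, nausea, vomiting, diarrhea, rash, fatigue | ≤ Grade 1, baseline, or tolerable Grade 2 |

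Table 6 therefore differs from its own footnote as well as from Section 6. Grade 4 neutrophils lasting more than 7 days agree on action but still differ on recovery grade.

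**Reach into evaluability**

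Section 5.1.3 counts a patient for the DLT assessment if the minimum safety requirements are met and/or a DLT has occurred, so the 75% dosing test does not decide whether a patient with a DLT counts. It can matter for a patient held for a toxicity that is not a DLT, such as afebrile Grade 4 neutropenia of 7 days or less. On a 28-day daily schedule:

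- Required doses: 0.75 × 28 = 21.
- 7 days held: 21/28 = 75.0%, meets the test.
- 8 days held: 20/28 = 71.4%, fails the test.

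If recovery to Grade 2 comes within 7 days and recovery to Grade 1 or baseline comes later, the choice of passage decides whether that patient enters the MTD-determining population. The documents give no recovery times, so how often this would happen cannot be stated.

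**The case against.** The best reply is that the texts can be read as specific beside general. The DLT sentence covers only Cycle 1 DLTs in dose escalation, while the tables are guidelines for Grade 3 or higher toxicity in any cycle and cohort. Its verb is permissive, so Table 6's Grade 4 discontinuation could be taken as limiting that permission. Table 5's neutrophil threshold and Table 6's tolerable Grade 2 could be toxicity-specific exceptions to a general default.

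Part of this stands. Different recovery thresholds for different toxicities are not in themselves an error. But the protocol states neither precedence, and the two readings give different actions: if the sentence overrides, patients may continue after Grade 4 events that Table 6 stops; if the tables override, the sentence is wrong for several DLTs. Calling the tables guidelines does not reconcile a mandatory restart rule in Section 6 with a lower bar in the tables, or Table 6 with its own footnote.

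A reader might also infer more than the text supports:
- That one DLT receives all three actions. Between the Section 6 sentence and the two tables the conflicts are pairwise. Section 6.2.1 is a separate liver rule and is not part of this comparison.
- That nearly every DLT path conflicts. Two rows above agree on action. Grade 3 rash or fatigue improving within 7 days, and Grade 3 nausea, vomiting or diarrhea controlled within 72 hours, are not DLTs at all.
- That Table 5 plainly allows full-dose resumption after Grade 4 platelets. The Grade 3 label makes that ambiguous.

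**Conclusion.** The protocol contradicts itself as written. The action conflict is established for three main groups: Grade 3 non-hematologic DLTs resolving within 7 days, Grade 4 non-hematologic DLTs outside Table 6's exceptions, and Grade 3 platelet DLTs with bleeding that recover within 7 days. The cover of Grade 4 platelets is an ambiguity rather than a shown contradiction. The restart conflict is established for neutrophils and for the five toxicities with the tolerable Grade 2 allowance, in any cycle.

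A reader might infer that dose-escalation decisions are compromised because DLT patients could fail the 75% test. The documents do not support that: a patient with a DLT counts under Table 4 footnote a and Section 5.1.3 whatever share of doses was taken. The consequences are inconsistent dosing after an event, by-dose summaries of dose modification that mix site practice with drug effect, and a possible effect on evaluability for some non-DLT holds.

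This rests on the current Version 4.0 text, not on its summary of changes. No view is taken on which clinical rule is right.

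**What to change.** The sponsor should reconcile Section 6, Table 5, and Table 6 with its footnote a in one edit:

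1. State whether the Section 6 sentence or the tables govern a Cycle 1 DLT, and make the other text refer to it.
2. State what applies when a DLT occurs at 30 mg, given the bar on lower doses, and how Section 6.2.1 relates to the DLT sentence.
3. State whether the platelet row of Table 5 covers Grade 4.
4. Give one recovery criterion per toxicity type, used identically in Section 6, the tables and the footnote.

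The clinical content is for the sponsor and its medical team to settle. The cost is wording in one section and two tables, handled as a protocol amendment. Sample size, the DLT definition and the MTD rule need no change.

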## 6.1 Dose Modifications Due to Hematologic Toxicity

Dose modifications due to hematologic toxicity are described in Table 5.

**Table 5 Dose Modifications Due to Hematologic Toxicities**

Event	AC176 Dose a
Neutrophil Count Decrease (ANC)	
ANC $<0.5 \times 10^9/L$ (Grade 4)	Hold dose until recovery to $\leq$ Grade 2 (ANC $\geq 1.0 \times 10^9/L$ ) b , 
 
• If resolved in <math>\leq 7</math> days, then resume without a dose reduction.
 
• If resolved in <math>>7</math> days but <math><2</math> weeks, then resume dose at one lower dose level.
 

Recurrence of ANC $<0.5 \times 10^9/L$ (Grade 4)	Hold dose until recovery to $\leq$ Grade 2 (ANC $\geq 1.0 \times 10^9/L$ ), then resume at 1 lower dose level b .
Platelet Count Decrease	
Platelets $<50 \times 10^9/L$ (Grade 3)	Hold dose until improvement to platelets $\geq 75 \times 10^9/L$ b 
 
• If resolved in <math>\leq 7</math> days, then resume without a dose reduction.
 
• If resolved in <math>>7</math> days but <math><2</math> weeks, then resume dose at 1 lower dose level.
 

Other severe and non-life-threatening toxicities (<math>\geq</math>Grade 3)	Hold or maintain dose at the treating physician's discretion.  Monitor at least weekly and manage accordingly.

a Any patients who require a treatment delay of more than 2 weeks due to treatment-related toxicity will be discontinued from study treatment unless the treating physician and the Medical Monitor agree that continued treatment at lower doses is in the best interest of the patient.

b Hold AC176 treatment; perform at least weekly complete blood count (CBC) with differentials until toxicity resolves (ANC recovery  $\geq 1.0 \times 10^9/L$  and platelets  $\geq 75 \times 10^9/L$ ).

Re-treatment criteria = ANC recovery  $\geq 1.0 \times 10^9/L$  and platelets  $\geq 75 \times 10^9/L$ .

CONFIDENTIAL

Study Drug: AC176

Sponsor/Development Innovations Study Number: AC176-001/GU 207

Final Protocol: 10 July 2023 Version 4.0

